3.2.2 Definition of Subgroups

Consistency of treatment effects across country (USA versus Japan) will be examined through the addition of a treatment-by-country interaction term to the statistical model for the primary efficacy endpoint. This is described in Section 3.8.1 of the SAP. No other subgroup analyses are planned.

3.3 Analysis Variables

3.3.1 Primary Efficacy Variable

- Change in HbA1c from baseline to Week 12

3.3.2 Secondary Efficacy Variables

- Change in HbA1c from baseline over time
- Change in FPG from baseline over time
- Percentage of subjects with HbA1c <7% post-baseline
- Change in systolic and diastolic blood pressure from baseline over time
- Change in body weight from baseline over time

3.3.3 Safety Variables

- Incidence of adverse events
- Percentage of subjects with a hypoglycemic event post-baseline
- Change in clinical laboratory parameters from baseline to each post-baseline assessment
- Shift in clinical laboratory parameters from baseline to each post-baseline assessment
- Change in vital sign measurements from baseline to each post-baseline assessment
- Change in ECG parameters from baseline to each post-baseline assessment

3.3.4 Other Variables

- Incidence of discontinuations and reasons for discontinuations from the study and, separately, from treatment
- Incidence of concomitant medications used

- Number of weeks on study drug
- Percentage of study drug taken relative to the planned dose

3.4 Subjects Disposition and Evaluability

3.4.1 Subject Disposition

Subject disposition will be summarized overall (all subjects) and then separately by country (USA and Japan). The overall number of subjects screened will be presented. The number of subjects randomized to treatment (intent-to-treat analysis set) and the number of subjects evaluated for safety (safety analysis set) will be presented by treatment group and overall. The number and percentage of subjects evaluated for efficacy (full and per protocol analysis sets) will be presented by treatment group and overall. The numbers and percentages of subjects completing and not completing the study through follow-up as well as the reasons for study discontinuations will be tabulated by treatment group and overall. In addition, the number and percentage of subjects completing and not completing treatment through week 12 as well as reasons for treatment discontinuations will be presented by treatment group and overall.

The demographic information for screen failures and run-in failures as well as reasons for their failures will be listed.

Screen failures are subjects who sign the informed consent but who have failed screening (e.g., subject did not meet eligibility criteria, subject withdrew consent) at Screening (Visit S1), Washout (Visit S2) or at the Phone Interview (Visit S3). Subjects who did not have study medication dispensed at the start of the Run-in Period (Visit S4) are also considered screen failures.

A run-in failure is defined as a subject who signs the informed consent but is deemed ineligible for the study (e.g., subject did not meet entry criteria, subject withdrew consent) after start of the Run-in Period but prior to randomization (Visit S5).

3.4.2 Protocol Deviations

All protocol deviations will be shown in a subject listing by treatment group. Subjects with major deviations identified as exclusions from the per-protocol analysis set will be indicated in the listing.

3.5 Demographics and Baseline Characteristics

If the full and intent-to-treat analysis sets are different from the safety analysis set then demographic and baseline characteristic analyses will be repeated using the full and intent-to-treat analysis sets.

3.5.1 Demographics

Subject demographics including age, gender, race, ethnicity, country and study center will be summarized by treatment group and overall for the safety analysis set.

Descriptive statistics will be provided for age (years). Frequencies and percentages will be tabulated for gender, race, ethnicity, country and study center.

3.5.2 Screening Characteristics

Subject baseline characteristics including screening body weight, height and body mass index (BMI) will be summarized by treatment group and overall for the safety analysis set.

Descriptive statistics will be provided for screening body weight (kg), height (cm) and BMI (kg/m^2).

3.5.3 Disease Characteristics

Subject disease characteristics including prior anti-diabetic treatment status, disease duration since diagnosis and episodes of symptomatic hypoglycemia per week will be summarized by treatment group and overall for the safety analysis set.

Descriptive statistics will be provided for disease duration since diagnosis (years). Disease duration is based on the year of first diagnosis and the year of informed consent signature (i.e., year of informed consent signature – year of first diagnosis). A value of 0 year means that the subject was diagnosed in the same year when informed consent was signed. Frequencies and percentages will be tabulated for prior anti-diabetic treatment status (whether treatment naïve or not) and for how many episodes of symptomatic hypoglycemia per week a subject experienced on average over the past year (0, 1, 2, 3 and more than 3).

3.5.4 Medical History

All significant medical and surgical history conditions will be coded using the Medical Dictionary of Regulatory Activities (MedDRA, Version 17.0) and will be classified by MedDRA system organ class (SOC) and preferred term (PT). Medical and surgical history conditions will be included in a subject data listing. Type 2

diabetes history and cardiovascular disease history will also be included in subject data listings.

3.6 Prior and Concomitant Medications

All medications will be coded using the World Health Organization Drug Dictionary (WHO-DD, Version B2 June 2014). A concomitant medication is defined as any medication that the subject has taken prior to enrollment and that the subject is expected to continue to take for some portion of the study as well as any medication other than the double-blind study medication that the subject takes during the course of the study. Medications used for controlling hypoglycemia will be recorded as concomitant medications in the eCRF.

Medications started prior to administration of the double-blind study medication will be identified as prior medications and included in a subject data listing only. Medications ongoing during the treatment period or started on or after administration of double-blind study medication will be summarized for the safety analysis set. The number and percentage of subjects who took at least one medication during the double-blind period as well as the number and percentage of subjects who took each type of medication will be presented for each treatment group and all active treatment groups combined. Medications will be listed according to their WHO-DD anatomic therapeutic chemical (ATC) class level 4 and preferred drug name within ATC class level 4 by decreasing frequency of incidence for all active treatment groups combined.

- **Rescue Medications**

Any medication given to treat hyperglycemia is considered a rescue therapy only if it is continued for 2 weeks or longer. Rescue medications will be identified by review of concomitant medication data, specifically the WHO-DD preferred drug name, indication field and duration of use (start and stop dates), during a blinded review of the data prior to database lock. Missing or partial start and stop dates for rescue medications taken during the double-blind treatment period are not expected, however if there are missing or partial start dates for rescue medications the same rules for handling missing or partial adverse event start dates will be applied (see Section 3.9.1). Missing or partial stop dates for rescue medications will not be imputed. Unless it is obvious from review of the partial stop date that the medication given to treat hyperglycemia could not have continued for 2 weeks or longer, it will be considered a rescue medication. Medications given to treat hyperglycemia with missing stop dates will be considered rescue medications.

Time to administration of first rescue medications will be summarized for the safety analysis set. Time to rescue medication use is derived by $[(\text{date of rescue medication} - \text{date of first study medication dose}) + 1 \text{ day}] / 7$. The number and percentage of subjects who took at least one rescue medication during the double-blind period as well as the number and percentage of subjects who took their first rescue medication during the intervals of ≤ 2 weeks, > 2 weeks - ≤ 6 weeks, > 6 weeks - ≤ 12 weeks and > 12 weeks from administration of first double-blind study drug will be tabulated by treatment group and all active treatment groups combined.

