Rescue medication for hyperglycemia should be prescribed by the investigator at any time it is deemed necessary for the well-being of the subject. During the 12 week treatment period, a review of diet and exercise counseling is suggested prior to prescription of rescue medication in the absence of specific medical indications for rescue medication. Rescue medication is suggested if, after a review of diet and exercise counselling:

1. more than 3 consecutive, daily, fasting SMBG measures are ≥ 270 mg/dL (15 mmol/L) from week 1 to week 6, or ≥ 240 mg/dL (13.3 mmol/L) from week 6 to week 12
2. fasting SMBG values are ≥ 250 mg/dL (13.9 mmol/L) and associated with clinical signs or symptoms of hyperglycemia (e.g. weight loss, blurred vision, increased thirst, or increased urination, or fatigue), and the signs or symptoms are severe

The investigator may provide rescue treatment with any approved medication for diabetes that is not otherwise contraindicated, with the exception of an SGLT2 inhibitor, as study subjects may already be taking a drug in that class as a consequence of being randomized to receive bexagliflozin.

Subjects who receive rescue medication due to poor glycemic control will continue to receive investigational product and standard of care per investigator decision, according to current treatment guidelines. Following the exit visit subjects will be advised to see their primary physician to undergo treatment to control their diabetes.

If hypoglycemia occurs in any subject prescribed rescue medication for hyperglycemia during the study, the total daily dose of the rescue medication should be reduced 50% or more at the discretion of the investigator.

OTHER SAFETY MONITORING ACTIVITIES

The safety monitoring activities will include assessment of vital signs, physical examinations, urinalysis, blood chemistry, hematology, adverse events, and concomitant medication use. The occurrence of blood, liver, or skin disorders will be monitored through laboratory testing and evaluation of adverse event documentation.

Adverse events of special interest as defined in the statistical analysis plan will include any clinical signs and symptoms that indicate adverse experience in the categories listed below. All such events must be appropriately documented within source documentation.

- Genital mycotic infections
- Urinary tract infections including urosepsis and pyelonephritis
- Diuretic effects including hypovolemia
- Hypotension episodes
- Hepatotoxicity

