3.1.6 Study Day

Subjects will be randomized and the first dose of investigational product during the Treatment Period will be considered Day 1. Study day for event dates prior to randomization and first dose will be determined as Study Day = (Event Date – Treatment Period First Dose Date). Study day for events after randomization and treatment period first dose will be determined as Study Day = (Event Date – Treatment Period First Dose Date) + 1.

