3.1.9 Analysis Visit Windows

Visit windows for study conduct are specified in footnote 1 of Table 1: Schedule of Events. Treatment period visits are planned for Day 1, Randomization (V1: Week 0),

Day 15 (V2: Week 2), Day 43 (V3: Week 6) and Day 85 (V4: Week 12). There is also a scheduled follow-up visit at Day 99 (V5: Week 14). A visit window of ± 3 days is allowed for all visits except for Week 0. Week 0 (Study Day 1, Randomization) is to be scheduled at 3 days after the last run-in visit (Visit S5) and can be extended to 5 days pending on HbA1c value availability.

For any unscheduled visits, Table 2 will be used to map the unscheduled assessments to the analysis visits prior to selection of records for analysis

Table 2: Nominal (Targeted) Time Points and Analysis Visit Windows

Assessment	Nominal (Targeted) Time Point	Analysis Visit Window (Interval in Study Days)
Baseline Assessments	Week 0 (Study Day 1)	\leq Day 1
Post-Baseline Assessments	Week 2 (Study Day 15)	Day 8 through Day 22
	Week 6 (Study Day 43)	Day 36 through Day 50
	Week 12 (Study Day 85)	Day 78 through Day 92
	Week 14 (Study Day 99)	Day 93 through Day 105

After mapping the data to the analysis visits, the following rules will apply unless otherwise specified for a particular analysis:

- If multiple records are available within a single analysis visit window, the record closest to the planned assessment day will be selected for analysis.
- If 2 records are equidistant from the target day, then the first record will be selected.
- If a subject has no record in an analysis window, the subject will be considered missing at that time point.

For subjects withdrawing early, the end of study data (early termination visit) will be mapped according to the analysis visit windows in Table 2 for summarization and analysis. However, if the visit does not fall within any of the analysis visit windows then the visit will be mapped to the next scheduled time point.

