3.7.2 Exposure to Study Treatment

Treatment duration (weeks on treatment) will be described in the safety analysis set using summary statistics. Treatment duration will be calculated as follows: $[(\text{date of last study medication dose} - \text{date of first study medication dose}) + 1 \text{ day}] / 7$.

Summaries will also include the number and percentage of subjects who were exposed for at least 2, $> 2 - \leq 6$, $> 6 - \leq 12$, and $> 12 - \leq 13$ weeks.

If the last dose date is unknown, the date of the last visit will be used.

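### SAP 3.7.2's exposure classes overlap and give under 2 weeks no class, and the day count used there and in 3.6 puts on-schedule visit days past the week cuts; a minor fault in two descriptive tables

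*SAP*

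**What the plan says.** **Exposure (SAP 3.7.2).** Weeks on treatment are (last dose date − first dose date + 1)/7. The text then reads "Summaries will also include the number and percentage of subjects who were exposed for at least 2", followed by >2–≤6, >6–≤12 and >12–≤13 weeks.

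**Rescue (SAP 3.6).** "Time to rescue medication use is derived by" the same expression, with the rescue date in place of the last dose date. Time since the first double-blind dose is cut into four intervals, with limits at 2, 6 and 12 weeks and each limit belonging to the earlier interval. For these the table gives the "number and percentage of subjects who took their first rescue medication during the intervals of" just described, per arm and pooled over the active arms. The section also says "Time to administration of first rescue medications will be summarized for the safety analysis set", without naming the statistic or a censoring rule.

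**Day numbering.** In SAP 3.1.6 "the first dose of investigational product during the Treatment Period will be considered Day 1". SAP 3.1.9 places the treatment visits at "Day 15 (V2: Week 2), Day 43 (V3: Week 6) and Day 85 (V4: Week 12"), each with a window of ±3 days.

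**Rescue rule (Protocol 3.2.3).** Rescue is suggested, after a review of diet and exercise counselling, if "more than 3 consecutive, daily, fasting SMBG measures are" at or above 270 mg/dL up to week 6, or 240 mg/dL from week 6 to week 12. The investigator may also prescribe rescue at any time it is judged necessary.

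**The concern.** Class limits in a table should be exclusive, cover every subject, and match the visit schedule that gives the weeks their names. Here they do not.

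- In 3.7.2 one class is cumulative and the rest are intervals. A programmer following the text would produce percentages that sum to more than 100, with no row for subjects who stopped in the first two weeks.
- In both sections the count starts at 1 on the day of first dose, while the cuts are whole weeks. The SAP's Week 2, 6 and 12 visit days therefore lie just beyond the cuts of the same name. Visits are a natural time to start rescue, because Protocol 3.2.3 has the investigator evaluate SMBG values and measures FPG at each visit.
- The bounded rescue intervals last 2, 4 and 6 weeks, yet the table shows counts and percentages of subjects with no number at risk. A reader cannot tell a longer interval from a higher rate.

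What is at stake is the description of when rescue happened and how long subjects were treated. The start of rescue decides which HbA1c values leave the primary analysis (SAP 3.8.1), so its timing should be described accurately.

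**Working it through.** **1. Reproduce the SAP's visit days.** Study Day = (date − first dose date) + 1, so week w falls on Day 7w + 1: 7×2 + 1 = 15, 7×6 + 1 = 43, 7×12 + 1 = 85. These match SAP 3.1.9.

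**2. Put those days through the 3.6 formula.** The formula equals Study Day/7.

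| Visit day | Weeks as written | Interval as written | Weeks without the +1 | Interval without the +1 |
|---|---|---|---|---|
| 15 | 15/7 = 2.14 | >2–≤6 | 14/7 = 2.0 | ≤2 |
| 43 | 43/7 = 6.14 | >6–≤12 | 42/7 = 6.0 | >2–≤6 |
| 85 | 85/7 = 12.14 | >12 | 84/7 = 12.0 | >6–≤12 |

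All three target days fall in the next interval.

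**3. Allow for the ±3-day window.** For V2 the permitted days are 12 to 18. As written, Days 12–14 fall in the earlier interval and Days 15–18 in the later one. Without the +1, Days 12–15 fall earlier and 16–18 later. V3 (Days 40–46) and V4 (Days 82–88) behave the same way. Dropping the +1 therefore moves one of the seven permitted days at each visit.

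**4. Exposure classes.** A subject treated for 8 weeks is in both the at-least-2 class and >6–≤12. A subject treated for 10 days is in no class. At the upper end:

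- last dose on Day 82: 82/7 = 11.71
- last dose on Day 83: 83/7 = 11.86
- last dose on Day 84: 84/7 = 12.0

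All three are in >6–≤12, with a subject whose last dose was on Day 43 (6.14 weeks). Exactly 84 daily doses, the planned 12 weeks, also falls there.

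**5. Interval length.** In Study Days the bounded rescue intervals are 1–14, 15–42 and 43–84, that is 14, 28 and 42 days. The documents give no rescue rate, so a constant daily hazard h is assumed. With cumulative rescue c by Day 84, h = −ln(1 − c)/84, and the share in an interval is the difference of exp(−h·t) at its ends.

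| Assumed c | Days 1–14 | Days 15–42 | Days 43–84 |
|---|---|---|---|
| 2% | 0.34% | 0.67% | 0.99% |
| 10% | 1.74% | 3.39% | 4.87% |
| 30% | 5.77% | 10.56% | 13.67% |
| 70% | 18.18% | 27.05% | 24.77% |

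At c = 10% the underlying rate is the same in every interval, 0.88 first rescues per 100 subject-weeks at risk, although the percentages rise. At 70% the last interval no longer rises. A falling hazard reverses the pattern: daily hazards of 0.0020, 0.00075 and 0.0004 give 2.76%, 2.02% and 1.59%. The shape of the table thus depends on the hazard as well as on interval length, and the table gives nothing with which to separate them.

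**The case against.** **The day count is a convention.** The formula is the SAP's Study Day divided by 7. Days 1–14 are the first two weeks, Day 15 opens the third, and Day 85 does follow 84 days of treatment. This is fair. The problem is only that the cuts carry the names of visits whose target days lie on the other side. Visits held one to three days early stay in the earlier interval.

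**The consequences are small.** The tables are descriptive and on the safety set. The primary MMRM drops HbA1c values after the actual start of rescue, whatever interval it is tabulated in. All arms share the same cuts, so no bias between arms within an interval is shown. A summary of time to first rescue is also promised. All of this stands, although that summary is unspecified.

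**Two stronger readings that a reader might infer are not supported.**

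- *Rescue will appear to rise late by construction.* Step 5 shows that this depends on the hazard. The lower suggested glucose level after week 6 may raise rescue use, but that is a real effect of a protocol rule. Rates per subject-week would not remove it, and the 6-week cut already lies about where the level changes. Simulated flat glucose (assumed mean 175, between-subject SD 35, daily SD 15 mg/dL, automatic rescue after four consecutive high days) gives a falling table if 270 mg/dL is held throughout: 0.29%, 0.18% and 0.12%. With the change at week 6 the last interval reaches about 3.6%, but applying the pre-randomization exclusion for fasting glucose of 250 mg/dL or more on consecutive days cuts this to about 1.2%, roughly 1 of 80 subjects per arm. The glucose values are assumed and the rule is only suggested, so no fold increase should be quoted.
- *Completers cannot be identified.* SAP 3.4.1 tabulates subjects completing and not completing treatment through week 12, with reasons, by arm. The number under 2 weeks could also be found by subtracting the at-least-2 count from the safety set.

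**Conclusion.** The point stands as a minor drafting fault. The overlap in 3.7.2, the missing class below 2 weeks, and the grouping of last doses on Days 82–84 with mid-trial stoppers follow directly from the SAP's text and need no assumption. The shift in 3.6 is exact for all three target visit days; over the permitted window, four of the seven days at each visit fall in the later interval. How many subjects this touches cannot be stated, because the documents give neither a rescue rate nor the share of rescues that start at visits.

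The effect is confined to the within-arm time profile of rescue and to the exposure classes. The primary analysis and the comparison of arms within an interval are unaffected. The effect of unequal interval length is conditional on the hazard, and it supports adding a denominator, nothing more.

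**What to change.** **SAP 3.7.2.** Make the first class ≤2 weeks. State the limits in days and place the last cut below Day 82, so that everyone whose last dose is within the V4 window shares one class: Days 1–14, 15–42, 43–81, and 82 or later. The documents do not say whether a dose is taken on the V4 day. If the last dose may be the day before an early V4, the cut should be one day lower.

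**SAP 3.6.** Cut at each subject's actual V2, V3 and V4 dates, with a rescue on the visit date counted in the interval that ends there, and use the target day where a visit was missed. Dropping the +1 is simpler but, as shown, moves only one of seven permitted days. For each interval and arm, add the number at risk or first rescues per subject-week at risk. Name the statistic and the censoring rule for the time-to-rescue summary. The change in suggested threshold at week 6 needs at most a footnote, and no clinical rule is affected.

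**Cost.** SAP wording and reprogramming of Tables 14.1.3.2 and 14.1.4. No new data are needed, and the rescue table becomes slightly longer.

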3.7 Treatment Compliance and Exposure

3.7.1 Compliance with Study Treatment

Compliance rates during the treatment period will be derived with the following formula:

$$100 * ((\text{Total number of tablets dispensed} - \text{Total number of tablets returned}) / (\text{Expected number of tablets to be taken over a subject's extent of exposure in days}))$$

Expected number of tablets to be taken over a subject's extent of exposure is based on the date of first study medication dose and the date of last study medication dose [i.e., $(\text{date of last study medication dose} - \text{date of first study medication dose}) + 1$]. If a subject is lost to follow-up, and therefore does not have a date of last study medication dose, the last visit date will be used as the date of last study dose to determine the expected number of tablets to be taken and it will be assumed that the subject did not take any tablets since the last visit date.

Compliance rates will be presented for the safety analysis set using summary statistics and percentage for the frequency distributions (0- $< 20\%$, 20- $< 40\%$, 40- $< 60\%$, 60- $< 80\%$, 80- $< 100\%$, 100- $\leq 120\%$) by treatment group and overall.

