5.3 Selection and Timing of Dose for Each Patient

Prior clinical experience has shown bexagliflozin tablets in strengths up to 90 mg per tablet are safe and well tolerated. The highest planned dosage of 20 mg per day is not expected to produce serious drug-related adverse events. Doses of 10 mg and 30 mg bexagliflozin in the tablet formulation have produced near saturation of UGE and statistically significant FPG lowering activity in prior studies. The dose strengths of 5, 10, and 20 mg have been selected to evaluate safety and efficacy of bexagliflozin.

Dosing with bexagliflozin tablets, 5, 10, 20 mg or placebo, will be based on randomized assignment. All study subjects will be instructed to self-administer one tablet with water every morning prior to eating or drinking. There will be no change of dose during the 12-week treatment period.

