5.9.2 Investigational Product Kit

One investigational product kit contains a bottle of 90 bexagliflozin tablets, 5 mg, 10 mg, 20 mg, or placebo.

The label attached to each investigational product kit will contain the following information: the kit number, protocol number, product identification, blinded batch number, subject number, storage conditions, sponsor's name and address, CRO or ICCR name and address, investigator's name, and the investigational drug caution statement.

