Participation in a clinical trial is voluntary. A subject can withdraw from the study at any time. The sponsor or investigator may terminate the study for medical or administrative reasons. If a decision is made to withdraw a subject from the study, no further investigational product should be administered. Even if the subject discontinues study medication, every attempt should be made to complete all required study evaluations and procedures. Reasons for all withdrawals should be recorded on the CRF. Examples of reasons for withdrawal include:

1. A protocol violation has occurred,
2. A serious or intolerable adverse event has occurred,
3. A clinically significant change in a laboratory parameter has occurred,
4. The sponsor or investigator terminates the study, or
5. The patient requests to be withdrawn from the study.

Subjects who do not complete the study but who have received investigational product should have a follow-up examination, including a physical examination, vital signs, ECG and clinical laboratory tests according to [Section 7](#).

Subjects who withdraw from the study will not be replaced.

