3.2 Analysis Populations and Subgroups

3.2.1 Definition of Analysis Populations

All Enrolled

All subjects who signed an informed consent form will be included in the all enrolled analysis set.

Full Analysis Set

All subjects who are randomized, take at least one dose of double-blind study medication, and have at least one post-randomization HbA1c measurement will be included in the full analysis set. All analyses of the full analysis set will be based on each subject's randomized assigned treatment.

Intent-to-Treat Analysis Set

All subjects who are randomized will be included in the intent-to-treat analysis set. All analyses of the intent-to-treat analysis set will be based on each subject's randomized assigned treatment.

Safety Analysis Set

All subjects who are randomized and take at least one dose of double-blind study medication will be included in the safety analysis set. Safety analyses will be based on the medication that was actually dispensed to each subject.

Per Protocol Analysis Set

The per protocol (PP) analysis set will include all subjects in the full analysis set who meet the study eligibility requirements as defined in Section 4 of the study protocol and have no major protocol deviations that affect the validity of the efficacy measurements. All analyses of the per protocol analysis set will be based on each subject's randomized assigned treatment. Major protocol deviations are defined as:

- Study drug compliance <80%
- Missing baseline or Week 12 HbA1c measurement
- Received prohibited medication including SGLT2 inhibitor, insulin or GLP-1 receptor agonists
- Randomization error
- Inappropriate unblinding (i.e., blind was broken (requested in IWRS) in absence of medical emergency or blind broken by unauthorized site personnel)
- Subject was dispensed with incorrect study medication

Subject exclusions will be determined on a case-by-case basis during a blinded review of the data prior to database lock. In addition, a blinded review of concomitant medications will be performed to further identify any other potential restricted medications.

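### Compliance is measured only up to the last dose, so the 80% per-protocol rule keeps subjects who stopped drug early

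*SAP*

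**What the plan says.** - **Compliance formula (SAP 3.7.1).** The rate is 100 × (tablets dispensed − tablets returned) / expected tablets. The expected number over a subject's "extent of exposure is based on the date of first study medication dose and the date of last study medication dose", that is, last dose date − first dose date + 1.
- **Variable list (SAP 3.3.4).** The variable is listed as "Percentage of study drug taken relative to the planned dose". No denominator is given there.
- **Per-protocol set (SAP 3.2.1).** There are six major deviations. The one that concerns adherence is "Study drug compliance <80" per cent. Another is "Missing baseline or Week 12 HbA1c measurement", with no condition that the sample be taken on drug. Stopping drug early is not on the list. "Subject exclusions will be determined on a case-by-case basis during a blinded review of the data prior to database lock".
- **Subjects who stop drug (Protocol 6.12).** "Even if the subject discontinues study medication, every attempt should be made to complete all required study evaluations and procedures".
- **Analysis (SAP 3.8.1).** The primary MMRM uses the full analysis set and treats post-rescue HbA1c as missing. Other off-drug values stay in. The same model is repeated on the per-protocol set as a sensitivity analysis.

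**The concern.** A per-protocol set is meant to show the result in subjects treated broadly as planned. Here the adherence test looks only at the days between first and last dose, so it cannot detect that dosing ended early. Nothing else on the list detects it either. Because the protocol asks stoppers to complete their visits, many of them should have a Week 12 HbA1c and so pass that criterion too.

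The rule can therefore keep a subject who took less than a quarter of the planned drug and remove one who took nearly four fifths of it. Off-drug Week 12 values in the active arms pull the per-protocol treatment differences toward zero. That weakens the one planned check of the primary result in adherent subjects.

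**Working it through.** **Inputs.** Planned dosing is one tablet a day ("self-administer one tablet with water every morning prior to eating or drinking", Protocol 5.3) for 12 weeks, so 84 tablets. Tablets dispensed: "One investigational product kit contains a bottle of 90 bexagliflozin tablets" (Protocol 5.9.2). The Week 12 target is Day 85 (SAP 3.1.9). Design assumptions are a difference of -0.5%, SD 0.9% and 70 evaluable per arm (Protocol 9.2).

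**The plan's own figure.** 0.5 / (0.9 × √(2/70)) = 3.287, and 3.287 − 1.960 = 1.327, giving power of 90.8% by the normal approximation (90.4% by noncentral t). The stated figure of about 90% reproduces and is not in dispute.

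**Compliance by last-dose day.** The subject takes every tablet until stopping and returns the rest, so tablets used = last-dose day.

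| Last dose | SAP 3.7.1 rate | Share of 84 planned | Days off drug at Day 85 |
|---|---|---|---|
| Day 20 | 20/20 = 100% | 23.8% | 65 |
| Day 28 | 28/28 = 100% | 33.3% | 57 |
| Day 42 | 42/42 = 100% | 50.0% | 43 |
| Day 56 | 56/56 = 100% | 66.7% | 29 |
| Day 67 | 67/67 = 100% | 79.8% | 18 |
| Day 68 | 68/68 = 100% | 81.0% | 17 |

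Since 0.80 × 84 = 67.2, any stop on or before Day 67 is below 80% of planned dosing, yet none fails the rule.

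**Imperfect adherence before stopping.** A Day 28 stopper needs 0.80 × 28 = 22.4, so 23 tablets, to pass. That is 23/84 = 27.4% of planned.

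**The opposite case.** A subject on drug for all 84 days who takes 66 tablets scores 66/84 = 78.6% and is excluded.

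**Unreturned tablets.** If a Day 28 stopper returns nothing, the SAP rate is 90/28 = 321%. Changing only the denominator to 84 gives 90/84 = 107%, which still passes. A planned-dose denominator is therefore not sufficient alone.

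**Subjects who leave through the exit visit.** Protocol 7.4.1 places that visit two weeks after the last dose. SAP 3.1.9 moves an early-termination visit that falls outside every window to the next scheduled time point. Last doses on Days 37–63 put the visit on Days 51–77, which is in no window and so maps to Week 12. Last doses on Days 64–78 put it on Days 78–92, inside the Week 12 window. Those with last doses on Days 37–67 took 44.0% to 79.8% of planned tablets and still pass. This route depends on the 3.1.9 mapping as well as on 3.7.1.

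**Size of the dilution.** Let f be the fraction of an active per-protocol arm wrongly kept with all effect lost. The difference is then −0.50 × (1 − f). The documents give no discontinuation rate, so f is an assumption.

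- f = 5%: −0.50 × 0.95 = −0.475%; power at 70 per arm falls from 90.8% to 87.7%.
- f = 10%: −0.50 × 0.90 = −0.45%; power falls to 84.1%.

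**The case against.** **Reach.** The strongest objection is that little depends on this. The primary MMRM and the dose-response contrasts use the full analysis set and never refer to compliance. The primary model already keeps off-drug values unless rescue was given, so the per-protocol analysis only fails to remove dilution that the primary accepts. This stands and confines the point to a supportive analysis. A reader might infer that the primary result or the choice of dose is biased; the documents do not support that.

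**Conflict with SAP 3.3.4.** A reader might take 3.3.4 as already fixing an 84-tablet denominator that 3.7.1 contradicts. It gives no denominator, and weeks on drug is listed there as a separate variable. The planned dose could mean one tablet a day while exposed. The two sections fit poorly together, but this is not a flat contradiction.

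**Visibility of stoppers.** It is tempting to say the compliance table hides early stoppers. It does not: Table 14.1.4 shows duration beside compliance, SAP 3.7.2 gives exposure bands, and SAP 3.4.1 reports treatment non-completion with reasons by arm. Compliance while on treatment is a legitimate descriptive measure.

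**Blinded review.** The case-by-case review could remove a subject nine weeks off drug. That is a real but partial safeguard: no listed criterion directs it to these subjects, and the one further review named is of concomitant medications.

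**Magnitude.** The gap between 80 randomised and 70 evaluable is not a forecast of ten stoppers with Week 12 data. Protocol 9.2 attributes it to possible drop-out and to safety evaluation, and drop-outs with no Week 12 value are excluded by rule. Total loss of effect two weeks after the last dose also conflicts with the protocol's statement that HbA1c reflects 2 to 3 months of glycaemia. These objections stand, so the figures are upper bounds for the assumed fractions.

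**Conclusion.** The point holds for the per-protocol set. As written, the 80% rule does not detect early stopping. A subject who adhered until a last dose anywhere up to Day 67 received less than 80% of planned dosing but is classed as compliant, and remains per-protocol if a Week 12 value exists and no other deviation applies. This is a stated rule that misclassifies subjects, not merely a missing detail.

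The consequence is modest and limited to the per-protocol sensitivity MMRM. With 5% to 10% of an active arm wrongly kept and all effect lost, -0.50% becomes at most about -0.475% to -0.45%. The dilution is smaller with HbA1c carry-over, where rescue makes later values missing, or where blinded review removes the subject. Greater dilution in one dose arm is possible if discontinuation differs by arm, but the documents give no basis for expecting that.

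**What to change.** Before unblinding:

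1. In SAP 3.2.1, base the 80% per-protocol rule on planned dosing: 100 × tablets taken / days from first dose to the scheduled Week 12 end of treatment, using 84 if drug was stopped early.
2. Add early treatment discontinuation, defined from the last-dose date, as an explicit major deviation, so that unreturned tablets cannot defeat the rule.
3. Keep the SAP 3.7.1 rate as a descriptive line labelled *compliance while on treatment*, and state the denominator in SAP 3.3.4.

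The cost is a few sentences of SAP text and one derived variable. No new data are needed, because dose dates and tablet counts are already used in SAP 3.7.1. The per-protocol set becomes slightly smaller and is selected on a post-randomisation event, as any per-protocol set is, so it should remain supportive.
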